The proposed research is specifically designed to investigate the ability of a novel tool to identify atypically developing infants from their typically developing peers. There will be an initial portion for usability feedback of hardware and software. For testing: For the first portion of the study (Part A) we will recruit up to 10 infants for analysis for up to two sessions each. After this initial testing, twenty-four infants will be recruited to participate, including 12 who are developing typically and 12 who are identified as at-risk for neuromotor delay. Infants with typical development will be at least 3 months and less than 11 months of age, score in the low-risk category on the Bayley Infant Neurodevelopmental Screener (BINS), score a greater than 85 on all sub-scales of the Bayley Scale of Infant Development (BSID-II), have no history of significant cardiac, orthopedic, or neurological condition, and gestational age at least 37 weeks. Infants at risk for neuromotor delay will be at least 3 months and less than 11 months of age (corrected for preterm birth if applicable), score in the moderate or high risk categories on the BINS, and score an 85 or less on the motor sub-scales of the Bayley Scale of Infant Development (BSID-II). In an effort to decrease variability of the data, infants in each group will be further stratified into an older group (8-10+ months) and a younger group (3-5 months).

Study duration

1) We estimate that it will take two years from the date of IRB approval to enroll all subjects and complete the study. 2) At minimum, some subjects may be asked to experienced the Gym 1x. At most, a subject will be asked to use the Gym for up to 5 consecutive days. Each day the infant will use the gym, both with and without toys, for 3 minutes. 3) 5/01/2015 - 8/01/2017

Characteristics of the Study Population

Target population

Two populations will be involved: 1. Infants exhibiting typical development between 3 months and 11 months of age 2 . Infants exhibiting atypical development (at-risk for neuromotor delay) between 3 months and 11 months of age.

Subjects enrolled by Penn Researchers

50

Subjects enrolled by Collaborating Researchers

0

Vulnerable Populations **Children Form**

Pregnant women (if the study procedures may affect the condition of the pregnant woman or fetus) Form

Fetuses and/or Neonates Form

Prisoners Form

Other

None of the above populations are included in the research study

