Prior to being assessed by the therapist, the parent or legal guardian will be consented. They will also be asked to fill out general surveys including, a demographic survey, and a case report form, and a user feedback survey which provides relevant information, on both the family's and infant's medical history and experience. After being assessed by a certified therapist for approximately one hour, both atypical and typical infants will be observed playing within the Gym. The environment will be prepared such that only items safe for infants will be in the testing and play areas. For the usability: The caregiver may be asked to closely observe and examine the hardware and the software of the system. The caregiver may then offer the toy to the infant for familiarization, observe the infant play and capture and upload a video of this interaction. The caregiver may be asked to complete a feedback and observation survey that will provide relevant information about the interaction and software and hardware experience. Part A) Data quantifying infants actions with and without toys will be collected in one or two sessions. Infants will be tested for their reaction to the gym without toys and then their reactions with 1 or multiple toys. The baby will be placed in the center of the gym. The baby will be allowed to settle and play for 1 minute then data will be collected again for 1-3 minutes. Each session will be recorded using the Microsoft Kinect camera. Arm/hand/leg position data will be collected with the Kinect camera, grasp pressure and forces will be collected, toy position and angular data will be collected via Kinect and inertial sensors, and central pressure data will be collected via the novel mat. Video data mapping their reaction may be collected using "Autism and Beyond" developed for research by Duke University. Part B) Data quantifying infant actions will be collected for 5 consecutive days under two conditions: with toys and without toys (control); the no toys condition will be tested first and the toy condition immediately after. The data from the no toy condition will be used to adjust the observations in the toy condition and will be used to account for the infants baseline actions per day. A test session will proceed as follows: First, the infant will be placed on his or her back at a pre-determined position on the gym mat in the no toy condition. Data will be collected for 3 minutes. The infant will be removed. The toys will be placed in the gym and adjusted for the infant reach; hanging toys will be placed at about 75% of the infants reach. After, the infant will be placed again with respect to the pre-determined position. To detect an infants intentional movement toward a specific toy, the location of each toy will be randomized within possible locations per toy type. The baby will be allowed to settle and play for 1 minute then data will be collected again for 1-3 minutes. Each session will be recorded using the Microsoft Kinect camera. Arm/hand/leg position data will be collected with the Kinect camera, grasp pressure and forces will be collected, toy position and angular data will be collected via Kinect and inertial sensors, and central pressure data will be collected via a pressure mat. General Procedure: A caregiver or parent will be seated at the head of the baby (out of baby's sight) to provide comfort if needed. Infants will be required to be alert and unhampered by clothing with their limbs free to move. They will be placed on their backs and allowed to roll or crawl as long as they stay within the perimeter of the device. If infants become frustrated (cries and is unsettled), the parent will be asked to pick them up and calm them. The trial will be restarted. If several attempts are unsuccessful, the session will be ended and attempted later in the day. We will take precautions to minimize the likelihood of participants experiencing any injury or discomfort. To avoid bumps, bruises or crashing into toys, participants will be supervised at all times by a trained study team member during CHOP sessions, including by a licensed pediatric physical therapist during developmental evaluations, and caregivers will be trained to place infants on their backs during home Gym play sessions. Caregivers will also be able to reposition their infants if he or she is uncomfortable.

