
The following documents are currently attached to this item:

There are no documents attached for this item.

Deception

Does your project use deception?

No

International Research

Are you conducting research outside of the United States?

No

Analysis Plan

We will identify a battery of metrics derived from kinematic and kinetic measurements of infant movement that are able to discriminate between atypical and typical infants and evaluate neuromotor impairments. Metrics quantifying one and two-handed reach and grasp actions as well as leg and body actions will be derived from the data. We will also determine the reliability/reproducibility of our methods across the repeated measurements taken in the home. We also will examine how each metric correlates with the BINS and BSITDIII scores. The key primary metrics are unimanual and bimanual arm use, leg use, grasp forces, arm position when being used, and arm velocity when used. Secondary measures will be center of pressure from starting position, toy speed, toy acceleration, toy tilt angle, arm synchronicity, leg synchronicity, leg distance to toy, and respective differences in the percentage of arm use for reaching and for grasping. Given our long-term goal of detecting the emergence or lack of emergence of multiple milestones in the development of infants, we will examine a variety of metrics. Some of these milestones are the emergence of hand dominance using the relationship between the right and left hands; the emergence of unimanual or bimanual reaching using the relationship of the hand position to the toy, the hand speed, the frequency of movements; the emergence of unimanual grasping using grasping forces, the emergence of undifferentiated bimanual grasping detected by monitoring when the right and left arms start to move together toward a toy, and the emergence of differentiated bimanual grasping. For each variable, we anticipate having 120 data points per second for a minimum of 180 seconds. Initially, kinetic metrics, and frequency of reaching and grasping will be summarized using means and standard deviations each day, to assess for variability. Intraclass correlations coefficients (ICC) will be calculated to examine reliability/reproducibility of each measurement over the 5 days. If the ICCs are relatively high (.9), we will average the 5 days to create a single summary figure for each measurement to test. Using these summary figures, we will first perform 2-sample t-tests or Wilcoxon rank sum tests on the averages or ranks of each metric respectively, where the two groups represent atypical and typical infants, stratified by age group. Given our stratified groups of younger/older and typical/atypical infants, we anticipate having relatively large differences across most measures. Should the ICCs be low, due to learning we will use a 2-factor ANOVA in repeated measures where day would be the repeated measure and age group and infant type would be the 2 factors. For non-normal distributions, such as many zeroes for the atypical group or other non-normal/skewed distribution, we will use either Poisson (log-linear) regression or a Negative Binomial (ZINB) regression. All analyses will be performed using SAS statistical software. As we are looking for proof of concept, we will be looking for relatively large differences between atypical and typical babies. In order to build a machine algorithm to analyze the baby data, we will build a test data set from publically held YouTube videos. We will pull YouTube videos from babies between the ages of 1 month and 12 months.

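### The non-normality fallback sends skewed continuous primary metrics to count regression, where a Poisson model at its default scale gives p-values that depend on the unit of measurement

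*Combined protocol and SAP*

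**What the plan says.** All of this stands in the Analysis Plan section of the combined protocol and SAP.

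- Primary metrics: "The key primary metrics are unimanual and bimanual arm use, leg use, grasp forces, arm position when being used, and arm velocity when used".
- Daily summaries, where continuous and count-type measures are named separately: "Initially, kinetic metrics, and frequency of reaching and grasping will be summarized using means and standard deviations each day".
- If the ICC over the five days is high, the days are averaged to one figure per infant and metric, and "we will first perform 2-sample t-tests or Wilcoxon rank sum tests on the averages or ranks of each metric respectively", stratified by age group.
- If it is low: "Should the ICCs be low, due to learning we will use a 2-factor ANOVA in repeated measures where day would be the repeated measure", with age group and infant type as the two factors.
- The next sentence is the fallback. For non-normal distributions, with many zeroes in the atypical group as the first example, "or other non-normal/skewed distribution, we will use either Poisson (log-linear) regression or a Negative Binomial (ZINB) regression".

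The section gives no units, variance scaling, robust standard error or significance level, and no rule for choosing between Poisson, negative binomial and Wilcoxon.

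**The concern.** Poisson and negative binomial likelihoods describe counts, which have no unit to choose. A force or a velocity does. In a Poisson model the variance is set equal to the mean, so recording the same movement in millimetres instead of metres makes the mean larger and tells the model that the data are relatively more precise. The estimated ratio between groups does not move, but its standard error, confidence interval and p-value do.

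The study aims to find metrics that separate atypical from typical infants. If a skewed continuous metric is analysed this way, the evidence that it discriminates can be created or removed by the choice of unit. The problem does not depend on where a significance threshold is set, because the test statistic itself changes.

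**Working it through.** **Inputs.** From the documents: 12 typical and 12 at-risk infants (Design), five test days in Part B (Procedures), and the metric list and fallback rule (Analysis Plan). The documents give no SD, CV, mean, effect size or alpha, so there is no planned figure to reproduce. Assumed for illustration: lognormal arm velocity, mean 0.2 m/s, CV of 0.3, 0.6 or 1.0, two-sided 5% level.

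**Algebra (no assumed values).** In a two-group Poisson log-linear model with n per group and group means m0 and m1, the log ratio is log(m1/m0) and its model-based SE at scale 1 is sqrt(1/(n·m0) + 1/(n·m1)). Multiplying all data by k leaves the log ratio unchanged, divides the SE by sqrt(k) and multiplies z by sqrt(k). From metres to centimetres k = 100, so z is multiplied by 10. From metres to millimetres k = 1000, so z is multiplied by 31.6.

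**Worked example** (n = 12, means 0.20 and 0.25 m/s, CV 0.6).

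- Log ratio = log(1.25) = 0.2231.
- SE in m/s = sqrt(1/2.4 + 1/3.0) = sqrt(0.4167 + 0.3333) = 0.866.
- m/s: z = 0.2231/0.866 = 0.258, p = 0.80.
- cm/s: z = 2.58, p = 0.010.
- mm/s: z = 8.15, p = 4e-16.
- Wilcoxon on the same data: p = 0.40 in all three units.

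**Rejection rate with no true difference** (Poisson at scale 1, 20,000 simulated datasets per CV, one value per infant).

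| CV | mean 0.2 (m/s) | mean 2 (dm/s) | mean 20 (cm/s) | mean 200 (mm/s) |
|---|---|---|---|---|
| 0.3 | 0% | 0% | 14% | 64% |
| 0.6 | 0% | 2% | 46% | 81% |
| 1.0 | 0% | 14% | 64% | 88% |

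A large-sample check agrees. The true variance exceeds the Poisson variance by the factor CV² × mean, so the rejection rate is about 2·Φ(−1.96/sqrt(CV² × mean)). At CV 0.6 and mean 20 the factor is 0.36 × 20 = 7.2, which gives 47%. At mean 200 it is 72, which gives 82%.

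**The opposite error.** At mean 0.2, scale-1 Poisson detects a true two-fold difference in 0% to 0.6% of datasets. An age-stratified rank test detects it in 99.9%, 78% and 45% (CV 0.3, 0.6 and 1.0), in any unit.

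**Negative binomial.** Forced onto the same kind of data, it rejects in 0% of null datasets at mean 0.2 and in 7% to 14% at means of 20 or more. In coarse units the estimated dispersion goes to zero and the model becomes Poisson. In fine units the unit effect levels off. ZINB was not fitted.

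**Variance correction.** A Pearson scale (t on 22 df) gives 4.8% to 5.1% null rejection at every mean.

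**Low-ICC branch.** Adding an infant intercept does not cure the problem. With 24 infants, 5 days and within-infant CV 0.6, scale-1 Poisson calls a null day trend significant in 0%, 3%, 48% and 83% of datasets at means of 0.2, 2, 20 and 200. A log-scale mixed model gives 4.7% to 5.2%.

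**The case against.** The strongest reply is that the sentence has a sound core. Its first trigger is excess zeroes, it names ZINB, and the plan analyses the frequency of reaching and grasping, for which count models are suitable. Arm use and leg use are not defined and might be counts. This stands: the fault lies in extending the rule to any other skewed distribution, and the plan's use of count models as such is not in question.

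A second reply is that a competent analyst would use a Pearson-scaled or robust variance. That would remove the Poisson unit dependence, but the plan names neither. The large percentages above therefore belong to Poisson at its default scale of 1. A reader might infer that every model named in the fallback fails as badly. The results do not support that: negative binomial levels off at about 7% to 14%, and ZINB is untested.

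A third reply concerns Wilcoxon. A reader might infer that a skewed metric with a high ICC falls under two competing rules, so that the analyst could pick after seeing the data. The text does not establish this. The fallback directly follows the low-ICC sentence and can be read as belonging to that branch alone, with Wilcoxon as the non-normal option in the high-ICC branch. It is an ambiguity to resolve. On either reading the problem with continuous metrics remains.

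Finally, this is a proof-of-concept study that looks for large differences and sets no alpha. The 5% level here is imported, but the sqrt(k) factor applies to any use of the test statistic.

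**Conclusion.** The point holds and should be fixed. As written, the rule assigns skewed continuous primary metrics to count models. For Poisson at scale 1 the unit dependence is exact: z changes by sqrt(k). Its practical size rests on assumed means and CVs. At CVs of 0.3 to 1.0, null rejection goes from 0% in m/s to between 64% and 88% in mm/s. For negative binomial the effect is smaller but present.

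The problem arises only if a continuous metric is in fact skewed and is sent to one of these models without a variance correction. It would not arise in this form for values that can be negative, because the count models could not be fitted to them. Procedures says that the no-toy data will be used to adjust the toy data but not how, so signed values are possible if the baseline is subtracted.

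The documents do not support saying that the estimated group ratio changes with the unit, or that ranks are the only valid remedy. In a check with a two-fold difference, Pearson-scaled Poisson had power of about 100%, 78% and 41% at CV 0.3, 0.6 and 1.0, against about 100%, 78% and 45% for the stratified rank test.

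**What to change.** Revise the fallback sentence in the Analysis Plan as follows.

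- **Counts.** Restrict Poisson, negative binomial and ZINB to true counts, such as numbers of reaches and grasps. Fit them to counts or totals, since five-day averages are generally not integers. Where daily rows are used, keep infant as the repeated unit (a random intercept, or GEE with a small-sample correction).
- **Skewed continuous metric, high ICC.** Use the Wilcoxon test that the plan already offers on the five-day averages, stratified by age (for example van Elteren), and state that it takes precedence over regression.
- **Skewed continuous metric, low ICC.** If values are strictly positive, use a log-scale mixed model with infant type, age group, day and an infant random intercept. If they are non-negative, a log-linear model with Pearson-scaled or robust variance, with infant kept as the repeated unit, is also acceptable. If they are zero-heavy or signed, use a rank or permutation test of infant-level summaries within age strata, stated as an exception to the averaging rule.

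Under the assumed settings these hold their level. Van Elteren rejects in 4.7% to 4.9% of null lognormal datasets and in 4.5% to 5.1% with 20% to 80% daily zeroes. The log-scale mixed model gives 4.9% to 5.2%.

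The cost is wording and standard procedures in SAS, which the plan already names; no new data are needed. There are four downsides. Rank results are less directly interpretable than mean differences. If the data are normal, van Elteren loses about 5 points of power (75% v 80% for an age-stratified t-test at an assumed 1.2 SD). Infant-level summaries do not show the day trend. Small-sample count models can stay slightly liberal at high ICC (8% for the corrected GEE at ICC 0.8 with extra day-to-day variation).

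### The count-model fallback states no unit of analysis, within-infant correlation or dispersion estimate, and its plain Poisson option gives wrong standard errors for infant type

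*Combined protocol and SAP*

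**What the plan says.** Under Study Design, "twenty-four infants will be recruited to participate, including 12 who are developing typically and 12 who are identified as at-risk for neuromotor delay", and each group is split into a younger and an older band. Under Procedures, Part B observes each infant on five consecutive days, with and without toys. Recording with toys lasts 1-3 minutes.

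The Analysis Plan then sets out three routes:

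- **High ICC.** "If the ICCs are relatively high (.9), we will average the 5 days to create a single summary figure for each measurement to test". The test is a t-test or a Wilcoxon rank sum test, stratified by age group.
- **Low ICC.** "Should the ICCs be low, due to learning we will use a 2-factor ANOVA in repeated measures", with day as the repeated measure and age group and infant type as the factors.
- **Non-normal data**, with many zeroes in the atypical group as the leading example: "we will use either Poisson (log-linear) regression or a Negative Binomial (ZINB) regression".

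The metrics that are true counts are those for which the "frequency of reaching and grasping will be summarized using means and standard deviations each day, to assess for variability". No significance level, expected count, variance or ICC is given anywhere.

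**The concern.** The first two routes keep the infant as the unit: one reduces each infant to a single figure, and the other names the repeated structure. The third changes the distribution and says nothing about structure. It also gives no rule for choosing between Poisson and negative binomial.

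This matters because infant type is a between-infant factor. The information on it comes from 24 infants, not from 24 x 5 = 120 infant-days. Ordinary Poisson or negative binomial regression on daily rows takes its precision from the 120 rows. Poisson also fixes the variance at the mean, so it ignores differences between infants even when the data are first summed to one total each.

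The plan's aim is to find metrics that separate typical from atypical infants. With standard errors that are too small, reach or grasp frequency could be declared discriminating when it is not.

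**Working it through.** The plan has no figure of its own to reproduce. The check asks how often each permitted reading of the fallback rejects when infant type has no effect.

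**Inputs from the documents:** 24 infants, 12 per type; two age bands; 5 days.

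**Assumptions:** 6 infants per age-by-type cell; two-sided nominal 5%; gamma-Poisson daily counts with mean m, infant CV .3-.8 (variance v_i = .09-.64) and day CV .5 (v_d = .25).

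**Step 1: Poisson on daily rows equals Poisson on totals.** With only infant-level covariates, the infant totals carry all the information in a Poisson log-linear model, so z is the same for both. Simulated rejection rates were identical. Dividing totals by 5 divides the model's information by 5, so on 5-day averages z is smaller by a factor of √5.

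**Step 2: size of the Poisson error.** The true variance of an infant's 5-day total, relative to what Poisson assumes, is

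φ = 1 + m·v_d·(1 + v_i) + 5·m·v_i

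The approximate actual level is 2[1 − Φ(1.96/√φ)]. For averages, replace φ by φ/5.

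| m | infant CV | φ | level, daily rows or totals | level, averages |
|---|---|---|---|---|
| 0.5 | .3 | 1.36 | 9% | 0.02% |
| 0.5 | .8 | 2.81 | 24% | 0.9% |
| 1 | .3 | 1.72 | 14% | 0.1% |
| 1 | .8 | 4.61 | 36% | 4% |
| 5 | .3 | 4.61 | 36% | 4% |
| 5 | .8 | 19.05 | 65% | 32% |
| 10 | .3 | 8.23 | 49% | 13% |
| 10 | .8 | 37.10 | 75% | 47% |

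Example, m = 10 and CV .8: φ = 1 + 10(.25)(1.64) + 5(10)(.64) = 1 + 4.1 + 32 = 37.1; √φ = 6.09; 1.96/6.09 = .32; level about 75%.

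Simulated null trials agree. Poisson on daily rows or totals gave about 8-34% at means of 0.5-1 (42-67% of daily counts zero) and about 33-77% at means of 5-10. Poisson on averages ran from near 0% to about 50%.

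**Step 3: negative binomial on daily rows.** This absorbs the overdispersion but not the correlation. With design effect 1 + (5 − 1)·ICC, the approximate level is 2[1 − Φ(1.96/√DE)]: 9.8% at ICC .1, 14.4% at .2, 18.6% at .3, 25.8% at .5 and 36.1% at .9. Simulation gave about 6-24% at means of 0.5-1 and about 8-38% at higher means. The 38% is from a setting with no day-to-day variation and an ICC of about .87.

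**Step 4: zero inflation.** ZINB on daily rows as independent, with means of 3-10 and 0-30% excess zeroes (five settings, 300 trials each), rejected in 15.5-25.8%. Modelling the zeroes does not replace modelling the infant.

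**Step 5: readings that behave.** Negative binomial on one total per infant gave about 7-9%, the excess being small-sample Wald error. Quasi-Poisson on totals with a t reference on 24 − 3 = 21 degrees of freedom gave about 2-7%. Poisson GEE clustered on infant, with bias-reduced standard errors and t(21), gave 3.0-5.8%.

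**The case against.** The strongest reply is that the plan is silent, not wrong. The fallback sentence follows two routes that respect the infant, and it can fairly be read as a change of distribution inside them. A reader might infer that the sponsor has decided to treat daily counts as independent. The text does not say so, and that inference should not be drawn. What stands is that the structure is unstated here, although it is stated for the ANOVA. Standard software treats rows as independent unless told otherwise.

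A reader might also infer that every version of the fallback has a false-positive rate several times 5%. That is not supported. Negative binomial on one total per infant, which the text permits, is only mildly inflated. Poisson on 5-day averages can be conservative. Poisson is also valid if there is no overdispersion at all (4.3% in simulation), although the plan's own trigger of skew or many zeroes makes that unlikely.

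Nor is it certain that the fallback will be used, since a Wilcoxon test is already available for non-normal summary figures. Most of the key primary metrics (forces, position, velocity) are continuous, so the point is confined to reach and grasp frequency. Finally, this is a proof-of-concept study looking for large differences. That lowers the stakes, but it does not repair a standard error of the wrong size.

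**Conclusion.** The point holds as one of under-specification, together with one named option that is unsound. Fixed-dispersion Poisson gives the wrong precision for infant type under ordinary between-infant variation, on daily rows and on totals alike. On averages, its error changes direction with the scale of the counts. Negative binomial or ZINB on daily rows is also too liberal unless the infant is modelled.

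The size depends heavily on the mean count. At the zero-heavy means that match the plan's leading example, the inflation is moderate. The very high rates need means of 5-10, where few daily counts are zero. All the rates rest on assumed means, CVs, cell sizes and a 5% level.

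Because this is a conditional fallback in a proof-of-concept study, it should be fixed before analysis, but it does not undermine the study as a whole.

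**What to change.** For count metrics (reach and grasp frequency), replace the fallback sentence as follows:

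- Delete the fixed-dispersion Poisson option.
- Analyse one total per infant by log-linear regression on infant type and age group, with estimated dispersion (quasi-Poisson or negative binomial) and infant-level degrees of freedom. Include an offset for log recording time, because recording with toys may last 1-3 minutes. Permutation of infant type within age band is an acceptable alternative.
- If daily counts are modelled, use a negative binomial or ZINB mixed model with a random infant intercept, or GEE clustered on infant with a small-sample correction.

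If a repeated-measures count model was intended all along, a clause saying so settles the correlation part; the Poisson option still needs an estimated dispersion or an infant effect.

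The cost is a change of SAP wording and slightly more analysis work in standard SAS procedures, with no new data. Intervals will generally be wider than under plain Poisson on daily rows or totals.
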